ClinicalTrials.gov PRS DRAFT Receipt (Working Version)

Last Update: 05/25/2022 18:02

ClinicalTrials.gov ID: [Not yet assigned]

Study Identification

Unique Protocol ID: TUN IRB4-10-13A

Brief Title: Physiological Responses to Osteopathic Manipulative Techniques in Healthy Young Adults

Official Title: Physiological Responses to Osteopathic Manipulative Techniques in Healthy Young Adults

Secondary IDs:

Study Status

Record Verification: April 2022

Overall Status: Completed

Study Start: October 4, 2013 [Actual]

Primary Completion: August 7, 2019 [Actual]

Study Completion: August 7, 2019 [Actual]

Sponsor/Collaborators

Sponsor: Touro University Nevada

Responsible Party: Principal Investigator

Investigator: [name] [[name]]

Official Title: Assistant Professor

Affiliation: Touro University Nevada

Collaborators:

Oversight

U.S. FDA-regulated Drug: No

U.S. FDA-regulated Device: No

U.S. FDA IND/IDE: No

Human Subjects Review: Board Status: Approved

Approval Number: IRB4-10-13A, IRB 8-09-17A

Board Name: Touro University Nevada IRB

Board Affiliation: Touro University Nevada

[contact]

Email: [contact]

Address:

Touro University Nevada
[name]
[name]

Data Monitoring: No
FDA Regulated Intervention: No

Study Description

Brief Summary: This study was designed to investigate the effect of selected osteopathic manipulative techniques (OMT) on cardiovascular functions in healthy young men and women.

This work addressed questions regarding physiological responses to OMT in maintaining the cardiovascular homeostasis by (1) measuring changes in the cardiac autonomic nerves activity, (2) measuring changes in cardiovascular parameters such as blood pressure, cardiac contractility, and heart rate, and (3) investigating if changes in the cardiac autonomic nerves activity were related to changes in blood pressure, cardiac contractility, or heart rate.

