This controlled not-randomized pilot study with repeated measures was conducted at the Touro University Nevada College of Osteopathic Medicine. Healthy 21-35 years old students and employees volunteered in the study. The experimental group received the three cranial osteopathic manipulative techniques, namely, occipital-atlantal decompression, occipital-mastoid decompression, and compression of the fourth ventricle, consecutively applied. This study included two control groups; one group received sham manipulations, and the second group did not receive any manipulations and was the non-touch group.

The computerized MP150 BIOPAC System was used for data collection and analysis. The skin electrodes were used for the one-lead ECG and impedance cardiography. Digital data were recorded during the entire experimental protocol. The blood pressure was measured manually before and after the experimental procedure using blood pressure cuff and stethoscope. Cardiovascular responses to OMT were evaluated by using the heart rate variability test (HRV), calculating changes in cardiac contractility, and comparing changes in pre- and post- blood pressure readings.

An analysis of variance (ANOVA) with a Bonferroni post-hoc test was used to evaluate treatment effects. The type I error rate (alpha) was set at 0.05.

Detailed Description: Healthy, 21-35 years old, male and female volunteers were recruited from Touro University students, faculty and staff using a brochure, poster, e-mail and personal conversation. Each participant signed an informed consent form. Participants were allowed to participate in multiple experiments (in the experimental and control groups) at least 7 days after the last experiment.

Each subject's weight and height were measured before the procedure. Anthropometric measures were used in cardiac impedance analysis, and as descriptive statistics of the studied population. All cardiovascular parameters were recorded by using a non-invasive method. We used disposable skin electrodes for impedance cardiography and a one-lead ECG.

The subjects were lying in the supine position and were asked to relax. All surface electrodes were connected to the computerized MP150 BIOPAC System for data recording. The duration of experimental protocol was about 30 minutes, and included three intervals: 10 minutes, pre-OMT rest phase (Rest); 8 to 12 minutes (about 10 minutes) of the OMT/Sham (Manipulations); and 10 minutes post-OMT recovery phase (Recovery).

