OMT and sham manipulations were administered by an osteopathic physician. The participant lied supine with physician seated at the side of the table facing the participant. Cranial OMT included three techniques and was administered in the following sequence: occipital-atlantal decompression, occipital-mastoid joint, and compression of the fourth ventricle. Control subjects received the sham manipulative procedure or relaxed in supine position (non-touch control). The total duration of OMT was controlled by an osteopathic physician and was

about 10 minutes.

Occipital-atlantal decompression: Patient is in the supine position. The operator places the tip of a finger against the posterior tubercle of the atlas and holds that bone anteriorly, preventing it from moving posteriorly with the condyles as the patient nods or tips the head forward. This will release tension between the occipital condyles and the first cervical vertebrae.

Occipital-mastoid joint decompression: The occipital squama is gently moved forward and upward (anteriorly and superiorly) with the pads of the long finger, and the mastoid process of the temporal bone is lifted anterolaterally with the pads of the index fingers. This technique decompresses the jugular foramen, which the vagus nerve passes through.

Compression of the fourth ventricle: Manipulation is accomplished by having the operator's hands cupped to receive the lateral angles and supra-occiput on their thenar eminences. Gentle compression medially is maintained (generally 2 to 3 minutes) until tissue changes, such as a softening or increased motion, are noted in the supraoccipital area.

Sham: The osteopathic physician placed his hands on the skull of the subject but did not influence cranial motion. The sham manipulative procedure (SMP) was administered for 10 minutes.

All manipulations were administered by the osteopathic physician; experiments were conducted at Touro University Nevada. Data were collected by a non-invasive method using BIOPAC Systems, Inc. Equipment MP150 for data acquisition and analysis. The protocol consisted of three phases: rest before manipulations (10 min), manipulations (OMT) (approximately 10 min), and recovery after manipulations (10 min).

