Data analysis: Most cardiovascular response variables were measured at baseline, immediately after manipulation ("immediate response"), and at the end of protocol ("after rest"). The immediate responses and at the end of protocol were calculated on a percentage basis relative to baseline to control some individual variations.

The percent response variables were each analyzed in a three-way analysis of variance (ANOVA) which included time ("Immediate response", "after rest"), treatment (cranial manipulation, sham), and sex (male, female) as fixed effects. For significant interactions in the ANOVA, a Bonferroni post-hoc test was used to compare treatment effects within time, sex, or both. The type I error rate (alpha) was set at 0.05. The relationships among dependent variables were described with Spearman correlations between percent response variables within. Analyses were done in Rv3.5.1 (R Core Team 2018).

Conditions

Conditions: Healthy Young Adults

Keywords: Osteopathic manipulations,
autonomic,
cardiovascular

Study Design

Study Type: Interventional

Primary Purpose: Basic Science

Study Phase: N/A

Interventional Study Model: Parallel Assignment

Number of Arms: 3

Masking: None (Open Label)

Allocation: Non-Randomized

Enrollment: 51 [Actual]

Arms and Interventions

Arms	Assigned Interventions

Experimental: Cranial OMT The experimental group received the three cranial osteopathic manipulative techniques, occipital-atlantal decompression (OAD), occipital-mastoid decompression (OMD), and compression of the fourth ventricle (CV4), consecutively applied.
	
Procedure/Surgery: Cranial manipulation group, or cranial osteopathic techniques (OMM) Cranial OMT procedure: Subjects were relaxed lying on the back for entire time of the research protocol (approximately 30 min). Osteopathic physician performed the osteopathic manipulations using his hands. The physician gently applied a small amount of force to the neck and head to release tissue tension until feeling a softening and warmth of tissues. Subjects experienced a sensation of slight pulling, releasing, or relaxing of the tissue.
 
Other Names:
 
• Cranial osteopathic manipulations, cranial osteopathic techniques, cranial OMT procedure

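### The stated three-way ANOVA lists two treatment levels for a three-arm design: non-touch has no stated analysis for variables read twice after baseline, and its role for blood pressure is unstated

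*Protocol*

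**What the plan says.** The aim, in the Brief Summary, is broad: "This study was designed to investigate the effect of selected osteopathic manipulative techniques (OMT) on cardiovascular functions". The same section says "This study included two control groups", one given sham, while "the second group did not receive any manipulations and was the non-touch group". The Detailed Description repeats this: "Control subjects received the sham manipulative procedure or relaxed in supine position (non-touch control". Study Design counts three arms, and the Arms and Interventions table lists non-touch as a separate no-intervention arm.

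Two sentences describe how arms are compared.

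- Brief Summary: "An analysis of variance (ANOVA) with a Bonferroni post-hoc test was used to evaluate treatment effects". No groups or factor levels are named.
- Detailed Description, Data analysis: the percent-response variables go into a three-way ANOVA with time (two post-baseline readings), "treatment (cranial manipulation, sham), and sex (male, female) as fixed effects". A Bonferroni post-hoc test follows a significant interaction.

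The only other analysis, Spearman correlations among the response variables, does not compare arms. Nothing in the document pools non-touch with sham or explains why it is absent from the model.

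**The concern.** A control arm was planned and run, yet the one model that is spelled out has no place for it. What is at stake is the question the analysis can answer. Sham involves the physician's hands on the skull. So far as the groups are otherwise comparable, OMT against sham takes out drift over about 30 minutes of lying still, and also any response to being touched. It estimates OMT over and above contact. It does not estimate OMT against supine rest, nor show whether contact alone does anything. If OMT and sham do not differ, a reader cannot tell no response at all from an equal response to touch. Only the non-touch arm can separate these.

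**Working it through.** The protocol gives no figure to reproduce on this point, so the check compares the design with the model and counts what the model covers.

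**Arms and contrasts.** Arms in the design (Study Design): 3. Treatment levels in the model (Data analysis): 2. Pairwise contrasts among k groups are k(k − 1)/2.

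- Design: 3 × 2 / 2 = 3 (OMT–sham, OMT–non-touch, sham–non-touch), with 2 treatment degrees of freedom.
- Model as stated: 2 × 1 / 2 = 1 (OMT–sham), with 1 treatment degree of freedom.

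**Cells, for variables with two post-baseline readings.**

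- Stated: 2 times × 2 treatments × 2 sexes = 8.
- Three-arm design: 2 × 3 × 2 = 12.
- Without a stated analysis: 12 − 8 = 4, all of them non-touch.

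**Blood pressure.** Outcome Measures gives one reading before the rest phase and one after recovery. There is no immediate response, so a model with time at two post-baseline levels cannot be fitted as written. Data analysis itself says only that most variables had all three readings. Without time, the design has 3 arms × 2 sexes = 6 cells, 2 of them non-touch. The two-level treatment list does not clearly govern this outcome, and the general ANOVA sentence neither includes nor excludes non-touch.

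**What the missing contrasts carry.** Exactly,

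(OMT − non-touch) = (OMT − sham) + (sham − non-touch).

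The stated model supplies the first term on the right. That term equals the left side only if sham and non-touch respond alike, which cannot be checked without non-touch data.

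**Can non-touch be given an immediate response?** The outcome time frame ties that reading to the end of manipulation, which non-touch does not have. The timeline supplies a match. Rest is 10 minutes and the next phase is "8 to 12 minutes (about 10 minutes) of the OMT/Sham (Manipulations", so manipulation ends at 10 + 8 = 18 to 10 + 12 = 22 minutes. The sham paragraph gives 10 minutes, hence 10 + 10 = 20. The Brief Summary says "Digital data were recorded during the entire experimental protocol", so a reading near 20 minutes should exist, provided that non-touch sessions followed the same timeline.

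**The case against.** Four arguments deserve an answer.

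1. *The general ANOVA sentence covers all three arms, or the explanation sits in a statistical analysis plan not seen here.* Either may be so. But that sentence names no groups and cannot supply a level that the detailed specification omits. Nor is this detail left for later: the protocol writes out the levels, and they do not match its own design.

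2. *Sham is the right comparator for selected techniques, and non-touch has no end of manipulation.* OMT against sham is a legitimate contrast for the technique-specific effect, and no text makes OMT against rest mandatory. The lack of an end point is a plausible reason for omission. It is not stated, though, and the continuous recording provides a way round it. This supports allowing a wording-only remedy; it does not remove the mismatch.

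3. *The trial is a completed, non-randomized, open-label pilot, so little hangs on it.* This limits what added contrasts can show. Confounding affects OMT against sham as well. It does not explain an arm with no stated role.

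4. *Adding the third arm is not as simple as it looks.* This stands. The Detailed Description allows the same person into several groups at least 7 days apart, and each session gives repeated readings. A plain factorial ANOVA with all interactions would leave the OMT and sham cell means untouched, but it would ignore that dependence, and its 95% intervals might not have nominal coverage. With a participant effect, non-touch data can move the OMT–sham estimate: if one person had OMT and non-touch and another had sham and non-touch, those sessions add an indirect comparison of OMT with sham.

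A reader might also infer that the non-touch data were discarded, that blood pressure was analysed without them, or that the reported results are wrong. The document supports none of these. It shows what is stated, not what was run, and gives no arm sizes or standard deviations from which to judge an effect on results.

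**Conclusion.** The point holds as an internal mismatch worth correcting. For variables read at both post-baseline times, the stated model covers 1 of 3 arm contrasts and 8 of 12 cells, and leaves OMT against non-touch and sham against non-touch without a stated analysis. For blood pressure the stated model does not fit, and the role of non-touch is open. The omission does not make OMT against sham invalid; it narrows what that contrast can be said to show. The conclusion rests on reading the bracketed list of treatment levels as complete, which is its natural sense. No size of effect on any result is claimed.

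**What to change.** Make treatment a three-level factor: cranial manipulation, sham, non-touch.

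- **Variables with two post-baseline readings:** take the non-touch immediate response about 20 minutes into recording. Fit a participant effect, and a session effect within participant, so that intervals allow for repeat participation and repeated readings.
- **Blood pressure:** compare the arms on the single pre-to-post change, with no time factor and with a participant effect.
- **Stated comparison:** keep OMT against sham at alpha 0.05, tested through its own one-degree-of-freedom contrasts, so that the third level does not alter what triggers the post-hoc step.
- **Added comparisons:** report OMT against non-touch and sham against non-touch with 95% confidence intervals, labelled post hoc, exploratory and open to confounding.

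**Cost.** No new data; a re-run. Averaged over sex, it adds 2 contrasts × 2 times = 4 unadjusted intervals per two-time variable, and 2 per blood pressure variable. If nothing differs and each interval has its nominal coverage, the chance that at least one excludes zero lies between 5% (fully dependent) and 4 × 5% = 20% (upper bound) for four intervals; if independent it is 1 − 0.95⁴ = 18.5%. For two intervals the range is 5% to 10%. They therefore support no confirmatory claim. The OMT–sham estimate may shift slightly once a participant effect is fitted, and the rerun should report that openly.

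**Alternative.** If non-touch was left out on purpose, state the reason, say how blood pressure was handled, and limit conclusions to OMT against sham. That is a change of wording only.

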
Sham Comparator: Sham manipulation The osteopathic physician placed his hands on the skull of the subject but did not influence cranial motion.
	
Procedure/Surgery: Sham manipulation The osteopathic physician placed his hands on the skull of the subject but did not influence cranial motion.
 
Other Names:
 
• Sham

No Intervention: Non touch group The control group whose members did not receive any manipulations.
	

Outcome Measures

Primary Outcome Measure:

1. Heart rate variability

The heart rate variability test was used to study the effect of OMT on heart rate and, by inference, on autonomic nervous system activity. A decrease in heart rate accompanied by an increase in vagal and decrease in sympathetic activity would indicate parasympathetic activation by OMT.

[Time Frame: The responses were measured immediately after the physician finished OMT/Sham (after Manipulations phase) and 10 minutes after post-OMT/Sham recovery phase (“Recovery”, “after rest”).]

2. Myocardial contractility

Changes in impedance cardiography parameters, such as stroke volume (SV) and cardiac output (CO), were used to evaluate the effect of OMT on myocardial contractility. An increase in cardiac output (CO) and stroke volume (SV) would indicate the stimulatory effect of selected OMT on myocardial contractility.

[Time Frame: The responses were measured immediately after the physician finished OMT/Sham (after Manipulations phase) and 10 minutes after post-OMT/Sham recovery phase (“Recovery”, “after rest”).]

3. Blood pressures

Systolic and diastolic blood pressure were measured by sphygmomanometer. A decrease in systolic blood pressure in response to OMT would indicate a decrease in vascular sympathetic tone.

[Time Frame: The blood pressure was measured manually before (before pre-OMT rest) and after the experimental procedure (after "Recovery" phase).]

Eligibility

Minimum Age: 21 Years

Maximum Age: 35 Years

Sex: All

Gender Based: No

Accepts Healthy Volunteers: Yes

Criteria: Inclusion Criteria:

Young adults

- Exclusion Criteria: Any pre-existing chronic cardiovascular diseases,
- Any pre-existing pulmonary diseases,
- Any pre-existing renal diseases,
- diabetes mellitus,
- endocrine disorders affecting the cardiovascular system,
- pregnancy,
- musculoskeletal conditions that can affect the use of the cranial OMTs, or
- acute illness that necessitates consulting a healthcare provider.

Contacts/Locations

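### Question (3): an unadjusted HRV–cardiac output correlation cannot by itself show an autonomic–contractility link, because cardiac output contains heart rate

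*Protocol*

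**What the plan says.** The Brief Summary of the protocol lists three questions. The third is "investigating if changes in the cardiac autonomic nerves activity were related to changes in blood pressure, cardiac contractility, or heart rate".

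The Data analysis paragraph of the Detailed Description gives one analysis of association: "The relationships among dependent variables were described with Spearman correlations between percent response variables within". The sentence stops there, without naming the grouping. The variables are percent responses, "calculated on a percentage basis relative to baseline to control some individual variations". The ANOVA in the same paragraph compares treatment, time and sex, so it does not address question (3).

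Under Outcome Measures:
- Primary outcome 1 takes heart rate and the autonomic reading from one test: "The heart rate variability test was used to study the effect of OMT on heart rate and, by inference, on autonomic nervous system activity".
- Primary outcome 2 uses impedance measures, "such as stroke volume (SV) and cardiac output (CO), were used to evaluate the effect of OMT on myocardial contractility".
- Primary outcome 3 is blood pressure, which the Brief Summary describes as a separate manual cuff reading.

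For the recording itself, the Brief Summary says: "The skin electrodes were used for the one-lead ECG and impedance cardiography". No pair of variables is excluded or adjusted, and shared components are not mentioned.

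**The concern.** Two of the pairs that belong to question (3) do not consist of separately measured quantities.

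- **HRV with CO.** CO is the product of heart rate and stroke volume. If autonomic change slows or speeds the heart and leaves SV alone, CO still moves with heart rate. The HRV–CO correlation is then non-zero although nothing has happened to SV. Because the protocol files CO under contractility, that correlation invites a reading as an autonomic–contractility link.
- **HRV with HR.** Both come from the beat intervals of one ECG. Many variability indices change with the mean interval even when relative variability is constant, so part of the correlation may be arithmetic.

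At stake is the answer to one of three stated study questions. A reader given only the unadjusted coefficients could not separate a relation with contractility from one with heart rate.

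**Working it through.** The protocol gives no correlation, power or variance figure, so there is nothing to reproduce.

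**Inputs**
- From the protocol: 51 enrolled, three arms. Equal arms would give 51/3 = 17 per arm and 34 for two arms. Equal arms and one row per participant are assumptions.
- Assumed: CO = HR × SV; SDs of percent change of 3–8% for HR and 5–12% for SV; an autonomic index correlated −0.6 with HR change and acting on nothing else. A two-sided 5% level serves as a yardstick only.

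**HRV–CO**

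On the percent scale 1 + ΔCO = (1 + ΔHR)(1 + ΔSV), so for small changes ΔCO ≈ ΔHR + ΔSV. Let a and b be the SDs of ΔHR and ΔSV, and ρ their correlation. Then

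r(index, CO) ≈ −0.6 × (a + ρb) / √(a² + b² + 2ρab), and Spearman = (6/π) · arcsin(r/2).

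- 5%/5%, ρ = 0: r = −0.6 × 5/7.07 = −0.424, Spearman −0.41.
- 3%/12%, ρ = 0: r = −0.6 × 3/12.37 = −0.146, Spearman −0.14.
- 5%/10%, ρ = −0.5: numerator 5 − 0.5 × 10 = 0, so r = 0.

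Simulation with 20,000 samples per setting (small-sample means lie slightly nearer zero than the formula; ranges reflect different random seeds):

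| SD of HR / SV | ρ | Mean rho, n = 17 | Significant, n = 17 | Significant, n = 34 |
|---|---|---|---|---|
| 5% / 5% | 0 | −0.38 to −0.39 | 36% | 66–67% |
| 5% / 8% | 0 | −0.29 | 21–22% | 41–42% |
| 5% / 10% | 0 | −0.24 | 16–17% | 30% |
| 3% / 12% | 0 | −0.13 | 8–9% | 12% |
| 5% / 10% | −0.5 | 0.00 | 5% | 5% |

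**HRV–SV and the partial correlations, same settings**
- With ρ = 0, index–SV averages about 0 and is significant in about 5% of samples.
- With ρ = −0.5, index–SV is 0.27 to 0.28 (20% significant at n = 17, 37% at n = 34), although the index acts on heart rate only. Unadjusted HRV–SV is therefore not fully safe alone.
- The partial Spearman correlation given HR change, (r_xy − r_xh·r_yh) / √[(1 − r_xh²)(1 − r_yh²)] on ranks, is significant in 5–6% of samples for both SV and CO in every row of the table.

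**HRV–HR**

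Let the index be proportional to (mean beat interval)^k with independent variation of its own, log SD v. Then r = −ka / √(k²a² + v²).

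- Weakest case, k = 1, a = 3%, v = 50%: −3/√(9 + 2500) = −0.06.
- Strongest case, k = 3, a = 8%, v = 15%: −24/√(576 + 225) = −0.85, Spearman −0.84.

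The protocol does not name the index, so the built-in part may be negligible or dominant.

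**The case against.** **The question (3) pairs are not all affected.** This stands. A reader might infer from the product CO = HR × SV that strong correlations are guaranteed throughout. The product does force HR–CO and SV–CO: with independent changes of equal SD both have a Spearman correlation of 0.69. But question (3) does not ask about those pairs. HRV–SV and HRV–BP share no component, since blood pressure is a separate reading: "The blood pressure was measured manually before and after the experimental procedure using blood pressure cuff and stethoscope". No strong correlation is assured for any HRV pair.

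**The 36% is not a false-positive rate.** This also stands. In that simulation the index really is associated with CO, through heart rate. The figure is the chance of detecting that association. The error lies in calling it contractility.

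**The analysis is descriptive, and CO is named together with SV.** The wording is descriptive, and alpha is not tied to the correlations. Primary outcome 2 looks for a rise in CO and SV together, so a CO change with SV unchanged would not meet it. This limits the treatment-effect reading, but that criterion does not govern the correlation analysis. These correlations are still all that is stated for question (3).

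**Adjusting for heart rate may remove the physiology of interest.** This is fair for HRV–HR and HRV–BP, because the protocol treats slowing with rising vagal activity as the signature sought. It does not weaken the contractility part, where the aim is to see what remains beyond heart rate.

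**Blood pressure is timed differently, from before the rest phase.** That is a separate matter. It creates no built-in correlation and adds nothing here.

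**Conclusion.** The point holds for two pairs. Unadjusted HRV–CO cannot by itself support an autonomic–contractility relationship, and HRV–HR needs a caution about shared beat intervals.

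For an index acting on heart rate only, the HRV–CO correlation at n = 17 runs from about −0.39 to −0.13 over the assumed SDs, and vanishes if HR and SV changes offset as in the last row of the table. These sizes rest on SDs, an index–HR correlation and a product identity that the protocol does not state. The direction of the argument needs only the identity.

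A reader might conclude that question (3) is bound to be answered yes on algebraic grounds. The document does not support that: HRV–SV and HRV–BP remain informative, and SV is already a named outcome. The treatment comparisons by ANOVA are untouched.

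**What to change.** The study is complete, so this is a change to analysis and reporting of data in hand.

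1. For the contractility part of question (3), base the conclusion on the HRV–SV correlation and on partial Spearman correlations of HRV with SV and with CO, given percent change in heart rate.
2. Do not offer unadjusted HRV–CO, HR–CO or SV–CO as evidence of a contractility relationship. If they are tabulated, state that CO contains heart rate and stroke volume.
3. Report HRV–HR with a note that both come from the same beat intervals. An HRV index normalised for mean beat interval is an optional sensitivity analysis, not a requirement.

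The cost is a few lines of code. The downside is fewer and weaker correlations to report.

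### Primary outcome 2 reads a rise in stroke volume and cardiac output as increased contractility, although a fall in vascular load can raise both with contractility unchanged

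*Protocol*

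**What the plan says.** All three primary outcomes are in the protocol under Outcome Measures.

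- Outcome 2 (Myocardial contractility) names its measures: "Changes in impedance cardiography parameters, such as stroke volume (SV) and cardiac output (CO), were used to evaluate the effect of OMT on myocardial contractility". It then states how a rise is to be read: "An increase in cardiac output (CO) and stroke volume (SV) would indicate the stimulatory effect of selected OMT on myocardial contractility".
- Outcome 1 (Heart rate variability): "A decrease in heart rate accompanied by an increase in vagal and decrease in sympathetic activity would indicate parasympathetic activation by OMT".
- Outcome 3 (Blood pressures): "A decrease in systolic blood pressure in response to OMT would indicate a decrease in vascular sympathetic tone". On timing: "The blood pressure was measured manually before (before pre-OMT rest) and after the experimental procedure (after 'Recovery' phase".

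The data analysis paragraph of the Detailed Description fits a separate model to each response: "The percent response variables were each analyzed in a three-way analysis of variance (ANOVA) which included time ('Immediate response', 'after rest'), treatment (cranial manipulation, sham". Sex is the third factor, and there is no heart-rate or blood-pressure term. Relations between outcomes are handled descriptively: "The relationships among dependent variables were described with Spearman correlations between percent response variables within".

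The Brief Summary gives the source of the recordings: "The skin electrodes were used for the one-lead ECG and impedance cardiography".

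**The concern.** Stroke volume depends on filling and on the load against which the heart ejects, as well as on contractility. Cardiac output also contains heart rate as a factor. The other two primary outcomes are concerned with exactly these quantities: outcome 1 with heart rate, outcome 3 with vascular tone. If the manipulation slowed the heart and relaxed the vessels, stroke volume and cardiac output would move for those reasons alone. Outcome 2 would still credit the movement to the myocardium.

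At stake is what one of three primary outcomes can conclude. A vascular effect could be reported twice: once correctly as lower pressure, and once wrongly as stronger contraction. The comparison with sham does not help here. It removes effects of time and rest that both groups share, but not heart-rate or vascular changes caused by the manipulation itself.

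**Working it through.** The protocol states no figure on this point, so there is none to reproduce. Two checks were made.

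**1. Identity.** CO = HR x SV. With proportional changes h in heart rate and s in stroke volume, the change in cardiac output is (1 + h)(1 + s) − 1. The stroke-volume rise that keeps cardiac output level is 1/(1 + h) − 1. The values of h are assumed, because the protocol gives none.

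- h = −3%: 1/0.97 − 1 = +3.1%
- h = −5%: 1/0.95 − 1 = +5.3%
- h = −8%: 1/0.92 − 1 = +8.7%
- h = −10%: 1/0.90 − 1 = +11.1%

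For example, heart rate −10% with stroke volume +8% gives 0.90 x 1.08 − 1 = −2.8% in cardiac output.

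**2. Illustrative elastance model.** SV = Ees(EDV − V0)/(Ees + Ea), with Ea = R x HR/60. Ees stands for contractility, EDV (end-diastolic volume) for filling, R for vascular resistance. Baseline values are all assumed: HR 65, EDV 120, V0 10, Ees 2.0, R 1.1. At baseline, Ea = 1.1 x 65/60 = 1.192 and SV = 2.0 x 110/3.192 = 68.9. With R down 10%, Ea = 1.0725 and SV = 220/3.0725 = 71.6, a rise of 3.9%. The last column, R x CO, is a rough proxy for mean pressure.

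| Assumed change | Contractility | SV | CO | R x CO |
|---|---|---|---|---|
| HR −5% | unchanged | +1.9% | −3.2% | −3.2% |
| HR −5%, EDV +3% | unchanged | +5.2% | 0.0% | 0.0% |
| R −10% | unchanged | +3.9% | +3.9% | −6.5% |
| HR −5%, EDV +3%, R −10% | unchanged | +9.2% | +3.7% | −6.6% |
| HR −5%, EDV +3%, R −10% | −5% | +7.3% | +1.9% | −8.3% |
| Ees +10% | +10% | +3.5% | +3.5% | +3.5% |
| Ees +10%, HR −10% | +10% | +7.3% | −3.4% | −3.4% |

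Rows 3 to 5 would all be read as stimulated contractility, although contractility is unchanged in two of them and lower in the third. Row 3 can hardly be told from row 6 on stroke volume and cardiac output; only the pressure column separates them. In row 7 contractility is higher but cardiac output falls.

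**3. Whether the analysis repairs the reading.** The separate models contain no heart-rate or load term, and a descriptive correlation does not alter the stated interpretation. Blood pressure is taken before the rest phase and after recovery, so a vascular contribution cannot be examined at the immediate-response time point.

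**The case against.** **The joint condition is a partial guard.** This stands. Slowing alone raises stroke volume but lowers cardiac output (row 1), and slowing with 3% more filling leaves cardiac output level (row 2). A reader might infer that longer filling from a slower heart is enough to trigger a false claim. The check does not support that: in the model, the false claim appears once load falls too.

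**Outcomes 1 and 3 are conditional.** They say how a decrease would be read and forecast neither its occurrence nor its size. This also stands. The point needs only that these are the effects the trial looks for.

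**The sentence runs in one direction.** A reader might infer that the protocol would reject a contractile effect if cardiac output did not rise. It does not say so. It attaches a meaning to a rise and none to its absence.

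**The parameter list is open, and relations between outcomes are examined.** The wording admits other impedance parameters, and the SAP, which is not at hand, may name some. The third aim in the Brief Summary and the Spearman correlations mean outcome 2 is not read wholly in isolation. But the sentence that draws the inference uses only cardiac output and stroke volume, and neither the open list nor the correlations put a condition on it.

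**Conclusion.** The concern holds as a fault in interpretation. As worded, outcome 2 can yield a false conclusion of stimulated contractility when lower vascular load, with or without longer filling, raises stroke volume and cardiac output. Conversely, a flat or lower cardiac output should not be taken as evidence against a contractile effect, since a fall in heart rate pulls it down by identity.

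The identity figures are exact for the heart-rate changes assumed. The model percentages depend on assumed values and show direction and rough comparability only. How often a wrong conclusion would arise cannot be computed from the protocol.

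A reader might go further and infer that the trial cannot answer its second question. That is too strong. The second aim in the Brief Summary also covers blood pressure and heart rate, which this point leaves untouched, and it does not dispute stroke volume and cardiac output as haemodynamic measurements. What is in doubt is the label on one component and the sentence that interprets it.

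**What to change.** Rename outcome 2 *stroke volume and cardiac output (impedance cardiography)* and delete the sentence that reads their rise as contractility. Interpret both measures alongside the heart-rate and blood-pressure changes, and state that blood pressure was not measured at the immediate-response time point.

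Optionally, if the stored ECG and impedance recordings allow it, add a timing index such as pre-ejection period as a supportive analysis. Label it post hoc, since the study is completed, and acknowledge that the index depends on load itself. The protocol does not show that the recordings can be re-scored in this way.

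Do not enter post-treatment heart-rate change as a covariate in the main treatment comparison. It may be a route by which the manipulation acts, and adjusting for it can bias the contrast, the more so in a non-randomised study.

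The required change costs wording only. Its downside is that a contractility claim can no longer rest on stroke volume and cardiac output alone.
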